# A. OBJECT

5000 women diagnosed of Adenomyosis(AM) with pathology or magnetic resonance image (MRI) will be enrolled from nationwide multicenter. Each center should recruite at least 200 patients.

— **PATHOLOGY**: Adenomyosis can be present diffusely throughout the myometrium, or confined to a discrete area. Upon sectioning the uterus, the myometrial wall appears thickened and often contains small hemorrhagic or chocolate colored areas representing islands of endometrial bleeding. The term cystic is used to describe either diffuse adenomyosis or adenomyomas for which with cysts >5 mm in diameter.

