### **B. STUDY DESIGN AND METHOD**

**—STUDY DESIGN:** A Prospective Multicenter Observational Cohort Study —**METHODS**:

**Period:**3 years, including 6 months for building up Network platform and database, 30 months for the follow-up with an interval of at least once every 6 months done for every patient and updating the database timely.

[figure not shown]

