## C. TECHNICAL ROUTE

1. **Build up database basing on the Network platform.** Licensed research centers recruite patients according to the consistent universal diagnostic criteria, and then extract and register clinical pathologic data from their medical records system after getting their informed consent. Limited sharing platform for the database entry would be built by expert network firms, making it available for sub-centers to access the database and download relevant data. Ultimately, on the premise of research results sharing, we could carry out clinical scientific research development and summary nationwide. [Picture 1.]

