#### Clinical pathologic data:

- 1). Characteristics of epidemiology (Age, reproductive history, menstrual history, body parameters)
- 2). Diagnostic criteria (pathology, transvaginal ultrasonography or magnetic resonance image)
- 3) Semeiology and evaluative criteria (vision algetic standard (VAS); pictorial blood loss assessment chart (PBAC))
- 4) Surgical approach and perioperative reproductive techniques program
- 5) Medical treatment
- 6) Reproductive choices and fertility outcomes
- 7) Symptom improvement, quality and satisfaction of Life
- 8) Malignant transformation
- 9) Menopausal symptoms and Hormone therapy
- 10) Systematic assessment of the side effects

Picture 1. Network platform (NP) and database Building

- 2. Based on the database imformations, 30-month follow-up will be done for every patient, trying to analyze the problems below: 1) The diagnostic strategies for AM;2) Selection of therapeutic scheme;3) Etiology of AM and endometriosis;4)The study of histology, molecular and genetics about AM and endometrial receptivity.
- 3. The Follow-up visits is standardized, and the contents include :1) The therapeutic efficacy, complication and side-effect of different treatments;2)The fertility outcomes of different reproductive choices;3) AM &menopausal symptoms and hormone therapy; 4) Relevant issues among malignant transformation of AM.
- 4. According to the data above, intensive training courses about AM will be organized regularly, finally propeling the formation of Expert Consensus and Clinical Guidelines about AM which suitable to chinese conditions.

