# E. QUALITY CONTROL MEASUREMENT AND RESULT PUBLICATION

- 1. Every center of the research possesses the competence of scientific research to conduct clinical studies. Special people from each center will be put in charge of the research and monitoring the whole procedure. The rights and interests, responsibility and obligation of all centers will be standardized with the research agreement.
- 2. The maintenance, secrecy and safety of Network platform and database will be guaranteed by Department of Obsterics and Gynecology, Peking Union Medical College Hospital.
- 3. Every center is responsible for the database building, and required to finish the prospective follow up for 200 patients at least.
- 4. The researchers' findings will be released in a paper published online.

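### With no consecutive-enrolment rule, no log of women not enrolled and no entry point before treatment, treatment comparisons can carry selection bias among women already treated at entry

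*Combined protocol and SAP*

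**What the plan says.** Section A defines the population and the numbers: "5000 women diagnosed of Adenomyosis(AM) with pathology or magnetic resonance image (MRI) will be enrolled from nationwide multicenter", followed by "Each center should recruite at least 200 patients". Section C, item 1, gives the recruitment rule: "Licensed research centers recruite patients according to the consistent universal diagnostic criteria". Centres then "extract and register clinical pathologic data from their medical records system after getting their informed consent".

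The list of data in section C covers treatment, including "Surgical approach and perioperative reproductive techniques program" and medical treatment, and also symptom improvement and quality of life. Item 3 of section C makes the efficacy, complications and side effects of different treatments part of the standardised follow-up.

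Section B labels the design "A Prospective Multicenter Observational Cohort Study" and provides 30 months of follow-up with contact at least every 6 months. Section E, item 3, says each centre is "required to finish the prospective follow up for 200 patients at least".

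Section D compares exposed and unexposed groups by chi-square test and relative risk with a 95% confidence interval. Where baseline characteristics differ, it adjusts for them by regression.

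The readable text has no rule for consecutive or all-comer enrolment, no enrolment window, no count of eligible women not enrolled, and no requirement that a woman enter before the treatment being compared.

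**The concern.** A centre that follows the text may choose which diagnosed women to approach. Where a woman has already been treated, staff can know both her treatment and how she has fared so far. If willingness to approach her, or her willingness to join, depends on both, the enrolled women misrepresent the treatments being compared. The duty to complete follow-up on at least 200 women also favours women expected to keep attending.

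At stake is one of the study's stated aims, the comparison of treatments. Women never registered leave no data, and without a log the enrolled share cannot be compared between treatments or centres. A planned total of 5000 also means that a modest distortion can reach statistical significance.

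**Working it through.** **1. What the plan's own figures give.** 5000 / 200 = 25, so there are at most 25 centres if each meets its minimum. The number of centres is not stated. The plan gives no response rate, effect size or registration rate, so the size of any bias cannot be derived from it.

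**2. Can women enter already treated?** Section A admits women on pathology and describes the findings in a cut uterus, so some can have had surgery before they qualify. Nothing limits entry to new or untreated cases. Section C has centres take treatment and symptom data from medical records. The route is open.

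**3. When does selective registration bias a comparison?** Let *s* be the probability of registration by treatment (A, B) and result (1 good, 0 poor). Then

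observed OR = true OR × (sA1 × sB0) / (sA0 × sB1).

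- Selection on treatment alone (sA1 = sA0, sB1 = sB0): the factor is 1, so no bias.
- Selection on result alone (sA1 = sB1, sA0 = sB0): the factor is 1, so no bias when there is no true effect. With a true effect the OR is still preserved, but the planned RR is not. With assumed responses of 60% and 40%, and 80% of good and 40% of poor results registered, the responses become 0.48/0.64 = 0.750 and 0.32/0.56 = 0.571. The RR moves from 1.50 to 1.31 and the OR stays at 2.25.
- Selection on both jointly: the factor differs from 1, and a difference appears where none exists.

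**4. Illustrative size.** Assumptions, none from the documents: true response 60% under both treatments, registration unrelated to result in B, 1000 women per group, two-sided 5% test. Observed response in A is pA = 0.6·sA1 / (0.6·sA1 + 0.4·sA0), RR = pA / 0.60, z = (pA − 0.60) / √[pA(1 − pA)/1000 + 0.6 × 0.4/1000], and the chance of significance is about Φ(z − 1.96).

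| Registered in A, good / poor result | Observed response in A | RR | z | Chance significant |
|---|---|---|---|---|
| 90% / 60% | 0.54/(0.54 + 0.24) = 69.2% | 1.15 | 4.34 | 99% |
| 85% / 70% | 0.51/(0.51 + 0.28) = 64.6% | 1.08 | 2.10 | 56% |
| 90% / 80% | 0.54/(0.54 + 0.32) = 62.8% | 1.05 | 1.28 | 25% |

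These rows treat every woman in A as open to such selection. If only a share *f* of the registered women in A were, the observed response would be f × pA + (1 − f) × 0.60, and the excess in RR shrinks in proportion to *f*.

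**5. Sensitivity to the assumptions.** Suppose 80% are registered everywhere except among poor results in A, where 70%, 60% or 40% are. At a 50% response the RR is 1.07, 1.14 or 1.33. Over responses of 30% to 70% it runs from 1.04 to 1.54.

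**6. Does baseline adjustment help?** Take two baseline strata with true responses of 30% and 70% and no effect, with 80% / 60% registered in A and 80% throughout in B. In the first, A shows 0.24/(0.24 + 0.42) = 36.4%, OR = (0.24/0.42)/(0.30/0.70) = 1.33. In the second, A shows 0.56/(0.56 + 0.18) = 75.7%, OR = (0.56/0.18)/(0.70/0.30) = 1.33. The false OR is the same within each stratum, so adjusting for the baseline factor leaves it in place.

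**The case against.** The strongest reply is that the design is prospective and the treatment results are to be gathered at standardised follow-up visits. Results that arise after registration cannot influence who is registered. This stands, and it confines the problem mainly to women already treated at entry. It does not close the problem, because no passage ties entry to a point before treatment. The pathway therefore overlaps with the undefined starting point for each woman.

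Four stronger readings are tempting, and the documents do not support them.

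- *Centres pick women out of their records.* Section C says that women are recruited and consent, and that records then supply their data.
- *The 200 is a quota that drives selection.* It is a minimum, and a number per centre is not itself a fault. The gap is the missing rule on whom to invite.
- *The comparisons are biased.* Only joint selection on treatment and result creates a false difference, and nothing in the documents shows that it occurs.
- *No analysis could address it.* A sensitivity analysis over assumed registration probabilities can bound the effect, although without a log those probabilities have no data behind them.

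It is also fair to say that the figure in section B is not shown, and that the research agreement mentioned in section E, item 1, which will set out centres' obligations, is not among the documents. Either might cover enrolment; nothing in the readable text says so.

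**Conclusion.** The point holds as a gap in the recruitment rule with a possible consequence. In the readable text, recruitment rests on diagnosis and a per-centre minimum alone, and previously treated women can enter. If their registration depends jointly on treatment and result, the treatment comparisons are biased and section D's adjustment does not correct it.

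The size is not known. With a 60% response, no true difference and the assumed registration rates above, the RR is about 1.05 to 1.15. The range moves with the assumptions and shrinks if few women are treated before entry. These figures show what could happen; they do not estimate what this study will find. The change is worth making because it is cheap and must be in place before enrolment begins.

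**What to change.** Amend section A and section C, item 1, along these lines:

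*From a fixed start date each centre invites every consecutive eligible woman, at her first attendance after that date, until at least 200 are enrolled and the overall target of 5000 is met, and keeps an anonymous log of eligible women not enrolled (age, route of diagnosis, treatment received or intended, reason).*

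Both conditions are needed. With fewer than 25 centres, stopping at 200 each would fall short of 5000. Inviting women at first attendance after the start date, and not only when they first meet the criteria, keeps previously diagnosed women in the study.

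In addition, record whether each woman was treated before entry, report the enrolled fraction by centre and treatment, and add to section D a repeat of each treatment comparison in women enrolled before the treatment under study.

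The cost is protocol wording and a short log entry for each woman not enrolled. Recruitment may be slower, and section B allots 6 months to set-up and 30 to follow-up with no separate recruitment period. The restricted comparison will contain fewer women and will leave out those whose diagnosis came from the operation being studied.

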#### -TRANSVAGINAL SONOGRAPHY:

- 1. Uterine enlargement—Globular uterine enlargement that is generally up to 12 cm in uterine length and that is not explained by the presence of leiomyomata is a characteristic finding.
- 2. Cystic anechoic spaces or lakes in the myometrium—The cystic anechoic spaces within the myometrium are variable in size and can occur throughout the myometrium. The cystic changes in the outer myometrium may on occasion represent small arcuate veins rather than adenomyomas. The application of color Doppler imaging at low velocity scales may help in this differentiation.
- 3. Uterine wall thickening—The uterine wall thickening can show anteroposterior asymmetry, especially when the disease is focal.
- 4. Subendometrial echogenic linear striations—Invasion of the endometrial glands into the subendometrial tissue induces a hyperplastic reaction, which appears as echogenic linear striations fanning out from the endometrial layer.
- 5. Heterogeneous echo texture—There is a lack of homogeneity within the myometrium with evidence of architectural disturbance. This finding has been shown to be the most predictive of adenomyosis.
- 6. Obscure endometrial/myometrial border—Invasion of the myometrium by the glands also obscures the normally distinct endometrial/myometrial border.
- 7. Thickening of the transition zone—This zone is a layer that appears as a hypoechoic halo surrounding the endometrial layer. A thickness of 12 mm or greater has been shown to be associated with adenomyosis.

#### -PELVIC MRI:

- 1. Thickening of the junctional zone(JZ)  $\geq 12 \text{ mm}$
- 2. Greatest JZ thickness to total myometrium ratio > 40-50% (connected to muscular hypertrophy).
- 3. Foci of high signal intensity running alongside the endometrium on T2 and sometimes also T1-weighted images that persist on Fat-Sat (FS)

### **B. STUDY DESIGN AND METHOD**

**—STUDY DESIGN:** A Prospective Multicenter Observational Cohort Study —**METHODS**:

**Period:**3 years, including 6 months for building up Network platform and database, 30 months for the follow-up with an interval of at least once every 6 months done for every patient and updating the database timely.

[figure not shown]
## C. TECHNICAL ROUTE

1. **Build up database basing on the Network platform.** Licensed research centers recruite patients according to the consistent universal diagnostic criteria, and then extract and register clinical pathologic data from their medical records system after getting their informed consent. Limited sharing platform for the database entry would be built by expert network firms, making it available for sub-centers to access the database and download relevant data. Ultimately, on the premise of research results sharing, we could carry out clinical scientific research development and summary nationwide. [Picture 1.]

#### Clinical pathologic data:

- 1). Characteristics of epidemiology (Age, reproductive history, menstrual history, body parameters)
- 2). Diagnostic criteria (pathology, transvaginal ultrasonography or magnetic resonance image)
- 3) Semeiology and evaluative criteria (vision algetic standard (VAS); pictorial blood loss assessment chart (PBAC))
- 4) Surgical approach and perioperative reproductive techniques program
- 5) Medical treatment
- 6) Reproductive choices and fertility outcomes
- 7) Symptom improvement, quality and satisfaction of Life
- 8) Malignant transformation
- 9) Menopausal symptoms and Hormone therapy
- 10) Systematic assessment of the side effects

Picture 1. Network platform (NP) and database Building

- 2. Based on the database imformations, 30-month follow-up will be done for every patient, trying to analyze the problems below: 1) The diagnostic strategies for AM;2) Selection of therapeutic scheme;3) Etiology of AM and endometriosis;4)The study of histology, molecular and genetics about AM and endometrial receptivity.
- 3. The Follow-up visits is standardized, and the contents include :1) The therapeutic efficacy, complication and side-effect of different treatments;2)The fertility outcomes of different reproductive choices;3) AM &menopausal symptoms and hormone therapy; 4) Relevant issues among malignant transformation of AM.
- 4. According to the data above, intensive training courses about AM will be organized regularly, finally propeling the formation of Expert Consensus and Clinical Guidelines about AM which suitable to chinese conditions.

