#### D. STATISTICS ANALYSIS

Categorical data is analyzed by Chi-square test, and continuous data is analyzed by T test. If the baseline characteristics are similar, the chi-square test can be used directly to compare the incidence rates between the group of exposure and the group of non-exposure, to conclude if there is a correlation between the exposure factor and outcome. In a meanwhile, calculate the relative risk and 95% confidence interval in order to further illustrate the degree of correlation. In contrast, if the baseline characteristics of exposure group and non-exposure group are different, multiple factor linear regression should be used to control the

mixing factors. If there is no time variation in the data, logistic linear regression can be used to adjust the baseline characteristics of the groups which are different in the model. If there are time variations in the data, Cox linear regression should be used to adjust the baseline characteristics of the groups which are different in the model.

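### Symptom improvement has no symptomatic denominator: section D compares whole exposure groups and does not name baseline VAS or PBAC as something to check or adjust for

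*Combined protocol and SAP*

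**What the plan says.** **Entry.** Section A states that "5000 women diagnosed of Adenomyosis(AM) with pathology or magnetic resonance image (MRI) will be enrolled from nationwide multicenter". Section C adds that centres "recruite patients according to the consistent universal diagnostic criteria". Neither sets a minimum for pain or bleeding.

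**Outcome.** The data list in section C includes "Semeiology and evaluative criteria (vision algetic standard (VAS); pictorial blood loss assessment chart (PBAC)" as item 3 and "Symptom improvement, quality and satisfaction of Life" as item 7. The follow-up content includes "The therapeutic efficacy, complication and side-effect of different treatments". No section defines improvement, gives a baseline threshold, or says which women form the denominator.

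**Analysis.** Section D has two branches. In the first, "If the baseline characteristics are similar, the chi-square test can be used directly to compare the incidence rates", with a relative risk and 95% confidence interval. In the second, "if the baseline characteristics of exposure group and non-exposure group are different, multiple factor linear regression should be used", with logistic or Cox models for the characteristics that differ. It does not list which characteristics are to be compared, does not say how similarity is judged, and does not mention baseline VAS or PBAC.

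**The concern.** A woman with no pain at entry cannot have less pain later, and a woman with normal bleeding cannot have a heavy-bleeding complaint relieved. Entry is by diagnosis, so the cohort may contain such women. It also covers fertility, menopause and several kinds of treatment, so the symptom-free share could well differ between treatments. The documents give no figures on this.

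If these women stay in the denominator as non-improvers, the observed improvement rate mixes two things: how well the treatment works, and how many of its recipients had anything to improve. Two equally effective treatments can then appear to differ. The same question arises in a Cox model for time to improvement, where a symptom-free woman can never have the event, and in a t test on change in score, where she contributes no possible reduction.

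Section C intends the results to inform treatment choice and a national guideline, and lets sub-centres download data. With the denominator left open, different analysts could settle it differently after seeing the results.

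**Working it through.** **Nothing to reproduce.** The documents give no improvement rate, effect size, symptom-free share or treatment-group size. Every input below is an assumption for illustration.

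**Inputs.** q = improvement rate among symptomatic women, 0.6 and equal in both groups. s1, s0 = symptom-free shares in the two groups. n = 500 per group.

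**Step 1: crude comparison, symptom-free women kept as non-improvers.** Observed rate = q × (1 − s). With equal q, crude RR = (1 − s1)/(1 − s0), whatever q is. For 30% against 10%, the rates are 0.6 × 0.7 = 0.42 and 0.6 × 0.9 = 0.54, so RR = 0.42/0.54 = 0.78. The true value is 1.00.

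| Symptom-free shares | Crude RR | Chance of a false significant difference |
|---|---|---|
| 20% v 20% | 1.00 | nominal level only |
| 15% v 10% | 0.94 | 0.16 |
| 20% v 10% | 0.89 | 0.48 |
| 30% v 10% | 0.78 | 0.97 |
| 40% v 10% | 0.67 | 1.00 |

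**Step 2: would section D's regression branch be reached?** Only if symptom status is among the characteristics compared. If it is, and if similarity is judged by a significance test (an assumption), an imbalance of 20% v 10% is detected with power 0.99 and one of 15% v 10% with power 0.67. Larger imbalances would go to regression. At 15% v 10% the direct comparison could go ahead about one time in three, with the smaller bias (RR 0.94).

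**Step 3: does regression remove the bias?** That depends on how the baseline symptom enters the model.

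- *Symptom-present indicator.* For 30% v 10%, the crude odds ratio is (0.42/0.58)/(0.54/0.46) = 0.62. Adding the indicator moves it to 1.00.
- *Linear baseline VAS.* VAS is set to 0 if symptom-free, otherwise drawn from a normal distribution (mean 6, SD 2) clipped to 1–10. The chance of improving is zero at VAS 0 and then jumps, which a straight line cannot follow. Simulation for 30% v 10%:

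| Rise in log-odds of improving per VAS point | Adjusted OR | False positives |
|---|---|---|
| 0 | about 0.82 | about 33% |
| 0.2 | about 0.89 (0.85 in a separate run) | 15% (20%) |
| 0.4 | about 0.93 (0.92 in a separate run) | 9% (10%) |

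**Step 4: restriction to symptomatic women.** Both observed rates become q, so RR = 0.6/0.6 = 1.00 in every scenario.

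**Step 5: equal shares, real effect.** Take true rates 0.7 v 0.6 and 20% symptom-free in both groups. The observed rates are 0.56 and 0.48. RR stays at 1.17, but the risk difference falls from 0.10 to 0.08. Power with 500 per group is 0.72, against 0.91 if all 500 were symptomatic. Restricting leaves 500 × 0.8 = 400 per group at 0.7 v 0.6. The pooled standard error is √(2 × 0.65 × 0.35/400) = 0.0337 and the unpooled one √((0.21 + 0.24)/400) = 0.0335. Then z = (0.10 − 1.96 × 0.0337)/0.0335 = 1.01, giving power of about 0.84. In this example the restricted analysis is the more powerful one despite its smaller denominator.

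**The case against.** Three stronger readings are tempting, and the documents do not support them.

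- *Section D simply compares incidence directly.* It does so only when baseline is similar. Unequal symptom-free shares are a baseline difference, and the largest crude biases above arise where the direct comparison should not be used. This stands, provided symptoms are among the characteristics checked; section D does not say that they are.
- *The plan counts symptom-free women as not improved.* No section says so. Item 7 is only a data heading. Such women could be left blank, excluded, or analysed by change in score. This stands too: the bias is conditional on a scoring choice that the plan leaves open.
- *Regression cannot repair the problem.* It can. Section D does not prescribe a linear VAS term, and a symptom indicator is an equally faithful reading that removes the bias. The residual bias under a linear term also depends on the assumed VAS gradient and shrinks as that gradient rises. For mean change, if expected change is proportional to baseline (for example, VAS halves), linear adjustment removed the bias in simulation: coefficient −0.01, against an unadjusted difference of 0.59.

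One could add that this is merely an undefined outcome. It is more than that. Even with improvement defined, the plan would still need to say who is at risk of improving, and the answer changes both bias and power.

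**Conclusion.** The concern holds in conditional form. The documents establish three things: entry without a symptom requirement, no symptomatic denominator for improvement, and no mention of baseline VAS or PBAC as characteristics to check or adjust for.

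The bias requires that symptom-free women are kept as non-improvers and that their share differs by treatment. It also requires either a crude comparison or an adjustment that misfits the jump at zero. Under the assumed 60% improvement, 500 per group and 30% v 10% symptom-free, the crude RR is 0.78 and a linear-VAS odds ratio runs from about 0.82 to 0.93. With a symptom indicator or with restriction, the bias is nil. Equal shares cause no bias when treatments are equal, but cost power when they differ. The actual size cannot be known from the documents. The change is worth making because it is cheap and settles the matter before data are seen.

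**What to change.** Add to section D:

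1. Improvement in pain is analysed among women with pain at entry, and improvement in bleeding among women with heavy bleeding at entry. The baseline VAS and PBAC cut-offs are fixed before analysis.
2. These analyses adjust for baseline VAS or PBAC whatever the observed balance between groups.
3. The number of women excluded for lack of the symptom is reported by group.
4. New onset of the symptom is analysed separately among women without it at entry.

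The sponsor should choose the cut-offs; the documents offer no basis for particular values.

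The cost is a few sentences and a smaller denominator for each symptom. No new data are needed beyond the VAS and PBAC scores already planned, provided both are recorded at entry.

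### Fertility outcomes by reproductive choice: the plan does not ensure that the main reasons for the choice are recorded or adjusted for, so the comparison is at risk of confounding by indication

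*Combined protocol and SAP*

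**What the plan says.** Section B describes the study as "A Prospective Multicenter Observational Cohort Study", with "30 months for the follow-up with an interval of at least once every 6 months". Section A sets enrolment at 5000 women. Nothing is randomised.

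Section C, numbered item 3, lists four contents of the follow-up visits. The second is "The fertility outcomes of different reproductive choices". Item 4 of the same section says the data should feed an expert consensus and clinical guidelines.

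The list of clinical pathologic data in section C has ten headings. Three bear on this point:

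- Heading 1 gives the baseline characteristics: "Age, reproductive history, menstrual history, body parameters".
- Heading 4 is "Surgical approach and perioperative reproductive techniques program".
- Heading 6 covers the reproductive choice and the fertility outcome, with no sub-items.

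Section D allows a direct chi-square test between exposed and unexposed groups when baseline characteristics are similar, with a relative risk and 95% confidence interval. When they are not similar it turns to regression. For data without a time element, "logistic linear regression can be used to adjust the baseline characteristics of the groups which are different in the model"; Cox regression takes the same role for time-to-event data. Section D gives no covariate list, no criterion for calling groups similar, and no sensitivity analysis for unmeasured confounding.

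**The concern.** In a non-randomised cohort the woman and her clinician choose the reproductive route. A partner factor, tubal disease, low ovarian reserve or a long time spent trying can plausibly steer that choice and also lower the chance of pregnancy. If so, part or all of a difference between choices would reflect who chose what, and not what the choice achieved.

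Two features of the plan leave this open. The data headings do not name these factors. The adjustment rule looks only at what has been recorded and only at what differs. Two groups could match on age and body measurements, differ sharply in infertility factors, and still go straight to a crude chi-square under section D.

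At stake is the reading of one of the four follow-up contents, in a study meant to inform guidelines. A large cohort gives no protection: this bias does not shrink with sample size, while the confidence interval around the biased estimate does.

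**Working it through.** **1. What is ensured, factor by factor.** The text of sections A to D was read for each factor.

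| Factor | Named in a data heading? | Nearest heading |
|---|---|---|
| Duration of trying | No | Reproductive history (1) or choices and outcomes (6) could hold it |
| Tubal status | No | Possibly reproductive history |
| Ovarian reserve | No | Age (1) is a partial proxy |
| Partner factor | No | None obvious |
| Reason for the choice | No | 4 and 6 record what was done, not why |

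**2. No figure to reproduce.** The plan gives no power, effect size or event rate for fertility, so the size of the bias can only be illustrated. Every input in steps 3 to 5 is an assumption, and the true effect of the choice is set to none (RR = 1).

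**3. First illustration.** Assume 30-month pregnancy of 25% with an added infertility factor and 55% without. If a share *p* of a group has the factor, its pregnancy rate is 0.25*p* + 0.55(1 − *p*).

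- *p* = 0.2: 0.05 + 0.44 = 0.49 (comparison group)
- *p* = 0.4: 0.10 + 0.33 = 0.43, so RR = 0.43/0.49 = 0.88
- *p* = 0.5: 0.125 + 0.275 = 0.40, so RR = 0.40/0.49 = 0.82
- *p* = 0.7: 0.175 + 0.165 = 0.34, so RR = 0.34/0.49 = 0.69

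**4. Second illustration, weaker factor.** Assume a base rate of 30% and one unmeasured factor that multiplies it by RRc. Then RR observed = [1 + p1(RRc − 1)] / [1 + p0(RRc − 1)].

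| Prevalence p1 v p0 | RRc = 0.5 | RRc = 0.7 |
|---|---|---|
| 30% v 20% | 0.85/0.90 = 0.94 | 0.91/0.94 = 0.97 |
| 50% v 20% | 0.75/0.90 = 0.83 | 0.85/0.94 = 0.90 |
| 60% v 10% | 0.70/0.95 = 0.74 | 0.82/0.97 = 0.85 |

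**5. Chance of a false significant result.** For the rates in step 4, this is the chance of a two-sided 5% test being significant in the biased direction, by the normal approximation for two proportions. With no bias it would be 2.5%. Group sizes are assumed, since the plan does not say how the 5000 divide between choices. In each range the lower value is for RRc = 0.7 and the higher for RRc = 0.5.

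| Prevalence | 500 per group | 1000 per group |
|---|---|---|
| 30% v 20% | 5% to 8% | 7% to 12% |
| 50% v 20% | 16% to 38% | 28% to 65% |
| 60% v 10% | 36% to 79% | 62% to 97% |

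**6. Reading.** Across steps 3 and 4 the spurious RR runs from 0.69 to 0.97. Swap which group carries more of the factor and it runs from 1/0.968 = 1.03 to 0.49/0.34 = 1.44. The mildest case is close to harmless and the strongest is not, and nothing in the documents says which applies.

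**The case against.** The strongest reply is that absence is being read from headings. The ten items are categories for extraction from medical records, not a field list. Reproductive history is not broken down and could well hold an infertility diagnosis and the time spent trying. The figures could not be seen for this review and might say more. This stands, and it limits the point to what the plan ensures. A reader might infer that section D cannot adjust for these factors; the documents do not show that.

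Four further inferences also go beyond the text:

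- **That comparing choices is a declared aim.** The phrase sits in item 3 of section C, the contents of follow-up visits. The problems to be analysed are in item 2, and fertility by reproductive choice is not among them. The comparison is a fair inference from section D's exposed versus unexposed scheme. The plan also does not define the choices or name assisted against natural conception.
- **That the gap could never be filled later.** The data come from medical records, so centres could in principle go back to them. Late retrieval across many centres would be laborious and uneven, which is a reason to define the fields early, not proof that the gap is permanent.
- **That the choice made by couples with the poorest outlook will look worst whatever its effect.** Even with the largest illustrated bias, a true RR of 1.5 would appear as 1.5 × 0.694 = 1.04, and a true RR of 2 as 2 × 0.694 = 1.39.
- **That the comparison is known to be confounded.** The illustrations ignore adjustment for age and reproductive history, which are recorded and would absorb some of the bias.

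It can also be said that the lack of a pre-specified confounder list affects every comparison in this registry. That is true, and it does not weaken the point here.

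**Conclusion.** The concern holds as a gap in what the plan guarantees. It does not ensure that partner factor, tubal status, ovarian reserve or duration of trying are recorded. It does not require adjustment for them if they are, and it permits an unadjusted test when the recorded characteristics look similar. A comparison of fertility outcomes between reproductive choices is therefore at risk of confounding by indication.

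The documents fix neither the size nor the direction of the bias. The illustrated range of 0.69 to 0.97 rests on three assumptions: no true effect, one unmeasured binary factor, and no adjustment through recorded variables. The conclusion also assumes that the choices will be compared under section D and that these factors influence both the choice and the outcome, which is plausible but not stated in the plan. The change is cheap and should be made, but the point does not undermine the cohort as a whole.

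**What to change.** During the 6 months set aside for building the database:

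1. Under data heading 1 or 6, add four fields: duration of trying to conceive at the date of the choice, and tubal status, ovarian-reserve result and partner factor as they already stand in the medical record. Give the last three an explicit 'not tested' level.
2. In section D, limit the fertility comparison to women seeking pregnancy.
3. Include the four fields and age in every fertility model, whether or not they differ between groups. For these outcomes this replaces the rule that adjusts only for differences and otherwise allows a crude chi-square.
4. Add a sensitivity analysis for unmeasured confounding, for example an E-value. With RR* the relative risk, inverted if below 1, this is RR* + √[RR*(RR* − 1)]. For an observed RR of 0.69, RR* = 0.49/0.34 = 1.44, and the E-value is 1.44 + √(1.44 × 0.44) = 2.24.

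The cost is four fields drawn from existing records and a short addition to section D. No new test or visit is needed. The downside is that some values will be 'not tested'. Women who have had less work-up may also be those who made a particular choice, so that level may track the exposure. The report should therefore acknowledge residual confounding even after adjustment.
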